#### **8.3.4.3      *Expectedness***

The Investigator will be responsible for indicating whether an adverse event (AE) is expected or unexpected. An AE will be considered unexpected if the nature, severity, or frequency of the event is not consistent with the patient population under study, the known risks of major surgery, or the risk information previously described for the study intervention.

#### **8.3.5      *Adverse Event Reporting***

Disease related events expected in this population may be reported by the investigator if they differ in nature or frequency from what is expected and appear to have a causal relationship to the test article. Adverse events must be reported in the subject's source documents. It is the Investigator's responsibility to forward to the site's IRB all SAE/SUSAR/unanticipated ADE reports.

#### **8.3.6      *Serious Adverse Event Reporting***

- The Principal Investigator must be notified within 1 business day of study team's knowledge of any event meeting the criteria and definition of a serious adverse event, regardless of attribution, occurring during the study or within 30 days of the last administration of the study related intervention.

03 Sep 2025

- The investigator must report all events meeting the criteria and definition of a serious adverse event that are unexpected and possibly related (definite, probable or possible) to study intervention as per the local IRB reporting requirements.
- Serious Adverse Events must be reported to the local IRB in accordance with the IRB's policies.
- The site must notify On Target Laboratories within 7 days of becoming aware of the event.

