## **8.3 Adverse Events and Serious Adverse Events**

### **8.3.1 Definition of Adverse Events (AE) and Adverse Device Events (ADE)**

An AE is any untoward medical occurrence temporally associated with the use of an investigational medicinal product, whether or not considered causally related to that product. An AE can be any unfavorable and unintended sign (for example, an abnormal laboratory finding), symptom, or disease. The Investigator, or his/her designee, will document AEs. Only AEs and ADEs considered causally related to the investigational product will be documented during the trial period.

03 Sep 2025

An ADE is an AE associated with exposure to a medical device, such as the camera system and NIR illumination in this study. Where the abbreviation AE is used in this protocol, it can be understood to incorporate ADEs where appropriate.

The Investigator should use his/her discretion in ordering additional tests as necessary to monitor the resolution of such events. Event outcome at resolution or at time of last follow up will be recorded as event resolved, resolved with sequelae, ongoing at discontinuation, or death. Events ongoing after the subject's last visit will be followed per the investigator's standard of care.

The Investigator should consider AEs both as they relate to the investigational product and as they relate to the procedures involved in the trial. The Investigator is responsible for determining the initial relationship and severity of adverse events.

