### **8.3.2     *Definition of Serious Adverse Events (SAE)***

A serious adverse event (SAE) is defined by federal regulation as any AE occurring at any dose that results in any of the following outcomes: death, life-threatening AE, requires hospitalization or prolongation of existing hospitalization, a persistent or significant disability/incapacity, or a congenital anomaly/birth defect. All SAEs will be documented during trial.

Important medical events that may not result in death, be life threatening, or require hospitalization may be considered an SAE when, based upon appropriate medical judgment, they may jeopardize the subject and may require medical or surgical intervention to prevent one of the outcomes listed in this definition. Examples of such medical events include allergic bronchospasm requiring intensive treatment in an emergency room or at home, blood dyscrasias or convulsions that do not result in subject hospitalization, or the development of drug dependency or drug abuse.

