#### **8.3.4.2      *Relationship to Study Intervention***

AEs must have their relationship to study intervention assessed by the clinician who examines and evaluates the participant based on temporal relationship and his/her clinical judgment. The degree of certainty about causality will be graded using the categories below. In a clinical trial, the study product must always be suspect.

- **Related** – There is evidence to suggest a causal relationship, and the influence of other factors is unlikely. The clinical event, including an abnormal laboratory test result, occurs within a reasonable time after administration of the study intervention, is unlikely to be attributed to concurrent disease or other drugs or chemicals, and follows a clinically reasonable response on withdrawal (dechallenge). Rechallenge information is not required to fulfill this definition.
- **Not Related** – A clinical event, including an abnormal laboratory test result, whose temporal relationship to study intervention administration makes a causal relationship improbable (e.g., the event did not occur within a reasonable time after administration of the study intervention) and in which other drugs or chemicals or underlying disease provides plausible explanations (e.g., the participant's clinical condition, other concomitant treatments). Or, the AE is completely independent of study intervention administration, and/or evidence exists that the event is definitely related to another etiology. There must be an alternative, definitive etiology documented by the clinician

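### The Related / Not Related definitions in 8.3.4.2 leave a gap, and because 8.3.1 records only related events, in-between non-serious AEs may be recorded or lost depending on the assessor; one trigger in 8.3.6 uses grades that are never collected

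*Protocol*

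**What the plan says.** **Grading (Protocol 8.3.4.2).** The section announces a single scale: "The degree of certainty about causality will be graded using the categories below". Two categories follow.

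- Related: "There is evidence to suggest a causal relationship, and the influence of other factors is unlikely".
- Not Related, first limb: an event "whose temporal relationship to study intervention administration makes a causal relationship improbable", and for which other drugs, chemicals or disease offer a plausible explanation.
- Not Related, second limb: the event is wholly independent of administration, or is definitely due to something else.
- The Not Related entry closes with a further condition: "There must be an alternative, definitive etiology documented by the clinician".

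The introduction to the scale adds a general stance: "In a clinical trial, the study product must always be suspect".

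**Recording (8.3.1).** "Only AEs and ADEs considered causally related to the investigational product will be documented during the trial period". For serious events, 8.3.2 says otherwise: "All SAEs will be documented during trial".

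**Reporting (8.3.6, second bullet).** The investigator reports SAEs that are "unexpected and possibly related (definite, probable or possible) to study intervention". These three grades are defined nowhere in the protocol.

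**Endpoint (sections 1.1, 3 and 9.1).** The first secondary endpoint is the incidence of all AEs, ADEs and SAEs from administration through Visit 3. It carries no causality condition.

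**The concern.** A causality grade is usually a label attached to an event that is already in the database. Here 8.3.1 makes it the condition of entry for non-serious events. A gap in the grading definitions is therefore also a gap in the data, and an event that was never written down cannot be recovered at analysis.

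The in-between case is foreseeable in this trial. The infusion may finish as little as 1 hour before imaging, on the day of surgery. The leading reactions listed in 2.4.1 (nausea 13%, vomiting 5%, abdominal pain 2%) have an obvious competing explanation in the operation, and 2.4.1 itself attributes AEs in the prior studies to surgery or the underlying disease.

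At stake are the comparability of the safety incidence from one assessor to the next, its agreement with the stated endpoint, and a reporting trigger in 8.3.6 that cannot be applied from the grades collected.

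**Working it through.** The plan states no figure on this point, so there is none to reproduce. The check is a comparison of text, followed by a note on scale.

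**Step 1: are the two categories exhaustive?** Cross timing with the strength of the alternative explanation.

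| Timing | Other cause | Related? | Not Related? |
|---|---|---|---|
| Plausible | Unlikely | Yes, given evidence of causality | No |
| Plausible | Definite and documented | No | Yes (second limb) |
| Improbable | Plausible, with a definitive cause documented | No | Yes (first limb) |
| Plausible | Plausible but unproven | No: other factors are not unlikely | No: timing is not improbable, and the other cause is not definite |

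The last row has no category. This does not depend on whether the closing condition applies to both limbs of Not Related or only to the second, because the first limb requires improbable timing in any case.

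**Step 2: what happens to an event in the last row?**

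- Non-serious: under 8.3.1 it is documented if the assessor calls it related and omitted if not. The endpoint would count it either way.
- Serious: 8.3.2 has it documented. The first bullet of 8.3.6 has the principal investigator notified whatever the attribution, 8.3.5 has all SAE reports forwarded to the IRB, and the third bullet of 8.3.6 requires reporting under IRB policy. Only the second bullet of 8.3.6 depends on the undefined grades.

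**Step 3: do the scales in 8.3.4.2 and 8.3.6 map onto each other?** Three grades cannot be read off a two-level scale without a rule, and none is given. The grade of possible would naturally hold the events in the last row, which 8.3.4.2 places nowhere.

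**Step 4: scale.** Input: n = 10 subjects (section 1.1).

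- One patient whose only event is omitted changes an incidence by 1/10 = 10 percentage points.
- Example: 1/10 has an exact (Clopper-Pearson) 95% interval of 0.3% to 44.5%; 0/10 has 0% to 30.8%.
- Background only, treating the rates in 2.4.1 as if they applied here: nausea at 13% gives 10 × 0.13 = 1.3 patients expected and 1 − 0.87^10 = 0.75 as the chance of at least one. Vomiting at 5% gives 0.5 and 0.40; abdominal pain at 2% gives 0.2 and 0.18.

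These last figures describe any occurrence, not ambiguous occurrences. The protocol does not give the ambiguous share or the share that would be graded Not Related. If a share *a* of the patients with nausea went unrecorded, the expected number would be 1.3 × *a*, that is, anywhere from 0 to 1.3 patients.

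**The case against.** **The protocol leans toward Related.** The rule that the product is always suspect, together with the demand for a documented definitive alternative, pushes an in-between event toward Related. This stands in part: systematic under-recording is not shown. But the definition of Related pulls the other way, and the general stance assigns no category. What remains is disagreement between assessors, of unknown direction.

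**Other sections record without a causality condition.** Section 8.1.2 has AEs recorded during the infusion, and 7.1 has new clinically relevant findings reported as AEs. Both pull against 8.3.1, but neither lifts its restriction. In 9.2.3 the causality qualifier most naturally attaches to ADEs rather than TEAEs, so the planned TEAE summary need not filter by causality. It can, however, only summarise what 8.3.1 has let in.

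**A reader might infer that possibly related SAEs go unreported to the IRB.** The documents do not support this. SAEs are documented, notified and forwarded without regard to the causality grade, and only one trigger is unclear.

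**A reader might also infer that recorded nausea could be 0% or 10–20% depending on the scale applied.** That fails for two reasons. The grades in 8.3.6 concern SAEs only, so a non-serious event faces no competing scale. And the 13% counts adverse reactions; 2.4.1 reports reactions during administration in 17% of patients, and reactions during a supervised infusion are often easy to attribute. The rate says nothing about how many events would be ambiguous.

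**The real driver is the filter in 8.3.1.** This is right. If all AEs were recorded, the grading gap could not change the all-AE incidence. It would still affect any table of related events and the second bullet of 8.3.6, so both need correcting.

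**Conclusion.** The point holds as an internal inconsistency with a limited consequence. The two causality definitions are not exhaustive, and 8.3.1 turns that gap into possible non-recording of non-serious AEs and ADEs that the endpoint is meant to count. Each omitted patient is worth 10 percentage points of incidence in a 10-subject study. How many there would be, and in which direction grading would err, cannot be derived from the protocol.

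The mismatch with 8.3.6 is a separate and smaller defect: one reporting trigger rests on grades that are not collected. It does not remove SAEs from the data or from IRB reporting.

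The conclusion assumes that 8.3.1 is followed as written. Safety is described without a formal test and the primary sensitivity endpoint is unaffected. The change should still be made before enrolment, because unrecorded events cannot be restored later.

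**What to change.** 1. **8.3.4.2:** make the scale exhaustive. Keep the full Not Related definition, state whether the documented alternative applies to both of its limbs, and count every event that does not meet that definition as related. This follows the section's own stance that the product is always suspect.
2. **8.3.6, second bullet:** use the same scale, or state how definite, probable and possible map to Related and Not Related.
3. **8.3.1:** replace the filter with recording of all AEs and ADEs from administration through Visit 3, with causality as an attribute of each event. This brings recording into line with the endpoint in sections 1.1, 3 and 9.1. Narrowing the endpoint to related events would remove the contradiction on paper but leave a judgement of causality as the gate to the data.
4. **9.2.3:** say whether the causality qualifier applies to ADEs only, and present all events and related events separately.

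The cost is wording in four sections and one CRF list. The downside is slightly more events recorded and tabulated as related, including perioperative events, in 10 subjects.

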### **8.3.7 *Reporting of Pregnancy***

Patients will be screened for pregnancy and excluded from the study if they are found to be pregnant.

03 Sep 2025

## 9 STATISTICAL CONSIDERATIONS

### 9.1 Statistical Hypotheses

- Primary Efficacy Endpoint:
  - The primary efficacy endpoint is the sensitivity of CYTALUX with NIR imaging for detection of malignant lesions. Sensitivity is defined as the proportion of fluorescent light positive lesions that are histologically confirmed to be cancer relative to the total number of lesions confirmed to be cancer.  
Sensitivity = (True Positive)/(True Positive + False Negative)
- Secondary Efficacy Endpoints:
  1. Incidence rates of all adverse events (AEs), adverse device effects(ADEs), and SAEs, from the time of CYTALUX administration through Visit 3
  2. Sensitivity for cancerous lesions for:
    - a. FR $\alpha$  positive lesions
    - b. FR $\beta$  positive lesions
- Exploratory Endpoints:
  1. Genomic evaluation of tumor inclusive of, but not limited to:
    - a. Estrogen receptor/progesterone receptor (ER/PR) status
    - b. HER2 status
    - c. Mismatch repair (MMR) status
    - d. POLE status
    - e. p53 status
    - f. CARIS whole genome sequencing
  2. The exploratory endpoint is the detection rate of CYTALUX with NIR imaging for identification of SLNs. The detection rate is the proportion of the patients with SLNs detected by CYTALUX and NIR imaging in all enrolled patients.

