	
confirmed to be cancer relative to the total number of lesions confirmed to be cancer.
 
Sensitivity = (True Positive)/(True Positive + False Negative)
 
Secondary Endpoints
 
 
1. Incidence rates of all adverse events (AEs), adverse device effects (ADEs), and SAEs, from the time of CYTALUX administration through Visit 3
 
2. Sensitivity for cancerous lesions for:             
 
a. FR<math>\alpha</math> positive lesions
 
b. FR<math>\beta</math> positive lesions
 
 
 
 
Exploratory Endpoints
 
 
1. Genomic evaluation of tumor inclusive of, but not limited to:             
 
a. Estrogen receptor/progesterone receptor (ER/PR) status
 
b. HER2 status
 
c. Mismatch repair (MMR) status
 
d. POLE status
 
e. p53 status
 
f. CARIS whole genome sequencing
 
 
 
2. The exploratory endpoint is the detection rate of CYTALUX with NIR imaging for identification of sentinel lymph nodes (SLNs). The detection rate is the proportion of the patients with SLNs detected by CYTALUX and NIR imaging in all enrolled patients.
 

Study Enrollment:	This study plans to enroll 10 subjects.
Study Population:	Adult subjects (>18 years old) undergoing surgery for endometrial cancer
Phase:	Investigator sponsored study (ISS)
Description of Sites/Facilities Enrolling Participants:	Department of Obstetrics and Gynecology Jordan Center for Gynecologic Cancer at Penn Perelman Center for Advanced Medicine [name]

03 Sep 2025

Description of Study Intervention:	CYTALUX™ (PAFOLACIANINE) INJECTION: folate analog ligand conjugated with an indole cyanine green-like dye as a solution in vials containing 1.6 mL at 2 mg/mL. Each subject will be administered a single intravenous dose of not less than 1 hour before and not more than 168 hours (7 days) before initiation of intraoperative NIR fluorescent imaging.  The imaging systems used in this study will be assessed for meeting the criteria for use with CYTALUX™ (PAFOLACIANINE) INJECTION.
Study Duration:	The recruitment period is estimated at 12 months.
Participant Duration:	The maximum duration a subject is in the study is approximately 2 months.

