### 1.3 Schedule of Activities (SoA)

Study Procedure	Screening Visit	Visit 1	Visit 2	Visit 3
	-30 days prior to surgery	-7 days to day of surgery	Day of surgery	4 weeks ±1 week post-surgery
Informed consent	X			
Medical history	X			
Confirmed surgical candidate	X			
Pregnancy test for patients of childbearing potential		X		
Study drug administration		X		
Surgery with associated procedures including intraoperative imaging and sentinel lymph node biopsy			X	
Histopathology assessment of resected tissue*			X	
Collection of genomic marker data**			X	
AE assessments		X	X	X
ADE assessments			X	X

\*Lesions will be resected during the surgery at Visit 2. Histopathology assessment and immunohistochemistry staining will be completed in accordance with local pathology procedures and timeline.

\*\*Genomic marker data obtained prior to surgery will be utilized, if available. If tissue is collected during surgery for genomic testing, the testing will be completed in accordance with institutional procedures and timeline.

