### 3 OBJECTIVES AND ENDPOINTS

OBJECTIVES	ENDPOINTS
Primary	
To assess the ability of CYTALUX™ (pafolacianine) injection used with near-infrared (NIR) fluorescent imaging for the detection of malignant tissue in subjects undergoing surgical resection for endometrial cancer	
Sensitivity is defined as the proportion of fluorescent light positive lesions that are histologically confirmed to be cancer relative to the total number of lesions confirmed to be cancer.
 
Sensitivity = (True Positive)/(True Positive + False Negative)

Secondary	

 
1. To assess the safety of CYTALUX in subjects undergoing surgery for endometrial cancer
 
2. To assess folate receptor (alpha and beta expression) in resected specimens
 
	
 
1. Incidence rates of all adverse events (AEs), adverse device effects (ADEs), and SAEs, from the time of CYTALUX administration through Visit 3
 
2. Sensitivity for cancerous lesions for: 
 
a. FR<math>\alpha</math> positive lesions
 
b. FR<math>\beta</math> positive lesions
 
 
 

Exploratory	

 
1. To assess the feasibility of using genomic markers to predict utility of CYTALUX with NIR imaging
 
2. To assess the feasibility of CYTALUX to identify sentinel lymph nodes
 
	
 
1. Genomic evaluation of tumor inclusive of, but not limited to: 
 
a. Estrogen receptor/progesterone receptor (ER/PR) status
 
b. HER2 status
 
c. Mismatch repair (MMR) status
 
d. POLE status
 
e. p53 status
 
f. CARIS whole genome sequencing
 
 
 
2. The exploratory endpoint is the detection rate of CYTALUX with NIR imaging for identification of sentinel lymph nodes (SLNs). The detection rate is the proportion of the patients with SLNs detected by CYTALUX and NIR imaging in all enrolled patients.
 

03 Sep 2025

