#### 8.1.3 Visit 2: Surgery

*[Purpose: To collect data on the performance of intra-operative molecular imaging]*

1. AEs and ADEs will be recorded during and following surgery.

03 Sep 2025

2. After the surgical site is visualized under normal light and/or palpation, the number and location of suspect lesions detected under normal light will be recorded on the schematic using an “O”.
3. Following the assessment by normal light, subjects will undergo fluorescence imaging of the surgical field. Suspect lesions detected under fluorescence imaging will be marked on the schematic using an “X”.
4. All identified suspect lesions will be marked on the schematic (“O”, “X”, or “⊗” as described in [Section 4.1.3](#)) and excised, at the discretion of the Investigator.
5. Sentinel lymph node biopsy will be performed at the Investigator’s discretion per the standard of care.
6. All excised lesions will be sent to the local laboratory for histopathology and immunohistochemistry staining. A unique identifier will be assigned to each excised lesion and the location of each will be recorded along with the unique identifier. If an organ/large section of tissue (e.g. uterus, omentum) with multiple lesions is excised *in toto*, one grossly positive lesion will be utilized for the purposes of calculating sensitivity and FR expression.
7. Histopathology, folate receptor expression, and genomic testing results will be recorded once data is received per institutional practices and timeline.

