### **8.3.3     *Unanticipated Adverse Device Effect (UADE)***

#### Risk of Misinterpretation

Errors may occur with the use of OTL38 during intraoperative fluorescence imaging to detect ovarian cancer and lesions in the lung, including false negatives and false positives. Non-fluorescing tissue in the surgical field does not rule out the presence of ovarian cancer or lesions in the lung. Fluorescence may be seen in normal tissues including bowel, kidneys, lymph nodes, and lungs as well as in inflamed tissues.

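### The exploratory sentinel-node detection rate divides by all enrolled patients, so patients with no SLN attempt or no imaging can count as detection failures

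*Protocol*

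**What the plan says.** The SLN endpoint is worded the same way in the Synopsis (1.1), in Section 3 and in Section 9.1: "The detection rate is the proportion of the patients with SLNs detected by CYTALUX and NIR imaging in all enrolled patients". It serves the exploratory objective "To assess the feasibility of CYTALUX to identify sentinel lymph nodes". The Synopsis gives the planned size: "This study plans to enroll 10 subjects".

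On who has the procedure, the protocol speaks in two ways. Section 8.1.3 says "Sentinel lymph node biopsy will be performed at the Investigator’s discretion per the standard of care". The Schedule of Activities (1.3) lists at Visit 2 "Surgery with associated procedures including intraoperative imaging and sentinel lymph node biopsy", with no mention of discretion. No inclusion criterion in Section 5.1 requires a planned SLN procedure.

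On who stays in the count, Section 7.2 makes cancelled or rescheduled surgery a possible reason for withdrawal. Patients who were dosed and then withdrawn are not replaced; patients never dosed may be.

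For contrast, Section 9.2.2 limits the primary analysis to patients who received the drug and were evaluated under NIR light during surgery. No such limit is attached to the SLN rate.

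**The concern.** A detection rate is normally read as how often the agent finds the node when someone looks for it. Here the denominator also takes in patients in whom nobody looked: those given no SLN procedure at the surgeon's discretion, and those dosed but never imaged. They can only lower the rate, and by an amount that says nothing about CYTALUX.

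Two centres with the same agent performance and different habits on SLN biopsy would report different rates. With about 10 patients, each such patient moves the figure by 10 percentage points (1/10). A low result could lead a reader to drop the SLN question when the true reason was that few procedures were attempted.

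**Working it through.** The protocol states no target, expected value or precision for this rate, so there is no figure of its own to reproduce.

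**Inputs**
- Enrolled patients: N = 10 (Synopsis).
- Dosed but never imaged: k. The protocol gives no number; k = 1 is used as an example.
- Patients with SLN biopsy: m. The protocol gives no number; 4, 6, 8 and 10 are assumed.
- True detection among those attempted: 80%, also an assumption.

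**Step 1: patients never imaged.** A patient without NIR imaging cannot have a node detected by it. The highest possible rate is (N − k)/N. With k = 1 and a detection in all nine others, it is 9/10 = 90% (exact 95% CI 56 to 100), against 9/9 = 100% (66 to 100) among those imaged. This step needs no rule about biopsy.

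**Step 2: patients with no SLN procedure.** Suppose that only patients with SLN biopsy can count as detected. The protocol does not state this rule; it is a condition of the calculation. Then:
- highest possible rate = m/N
- expected rate at 80% detection = 0.80 × m/N

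| m | Perfect detection, all enrolled (exact 95% CI) | Perfect detection, attempted only (exact 95% CI) | Expected all-enrolled rate at 80% detection |
|---|---|---|---|
| 4 | 4/10 = 40% (12 to 74) | 4/4 = 100% (40 to 100) | 0.80 × 4/10 = 32% |
| 6 | 6/10 = 60% (26 to 88) | 6/6 = 100% (54 to 100) | 0.80 × 6/10 = 48% |
| 8 | 8/10 = 80% (44 to 97) | 8/8 = 100% (63 to 100) | 0.80 × 8/10 = 64% |
| 10 | 10/10 = 100% (69 to 100) | 10/10 = 100% (69 to 100) | 0.80 × 10/10 = 80% |

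**Step 3: reading the result.** The shortfall at 80% detection is 80 − 48 = 32 points at m = 6, 80 − 64 = 16 points at m = 8, and zero at m = 10. All of it comes from how many procedures were attempted.

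**The case against.** **The denominator fits a feasibility objective.** Section 3 asks about feasibility, and a rate over everyone enrolled is a conservative summary of that. The Schedule of Activities lists SLN biopsy without qualification, so all 10 patients may have it, and then there is no bias. Patients never dosed may be replaced. This stands as a reason to keep the all-enrolled figure. It does not make that figure a measure of how well the agent finds nodes, and Section 8.1.3 does not promise m = 10.

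**The m/10 cap is conditional.** Section 8.1.3 lists field imaging and SLN biopsy as separate steps, and nothing says that an unbiopsied patient cannot be recorded as having an SLN detected. If such patients can count, the cap in Step 2 falls away. This stands; only the loss from unimaged patients in Step 1 is free of that condition.

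**A stronger reading to resist.** A reader might infer that any fluorescing node counts as a success, because Section 8.3.3 warns that "Fluorescence may be seen in normal tissues including bowel, kidneys, lymph nodes, and lungs as well as in inflamed tissues", and that the rate therefore cannot measure SLN detection at all. The documents do not support this. The endpoint speaks of SLNs detected, not of fluorescing nodes. The warning is written for ovarian cancer and lung lesions and concerns normal tissue: a benign node that fluoresces is a false positive for cancer, but it may still be the sentinel node. It is true that the protocol names no way of establishing a node as sentinel independently of CYTALUX, and that the Appendix 1 form has no field for it. That is an operational definition not shown here, part of which could sit in the SAP or case report form. It is not a stated rule for miscounting.

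**Conclusion.** The concern holds for the denominator. As defined in three places, the SLN detection rate counts patients who were never imaged as failures. If detection requires a biopsy, it also counts patients with no SLN attempt as failures. Under that condition, and with the assumed 80% detection, the reported rate would be 32%, 48% or 64% for 4, 6 or 8 procedures among 10 patients, and unbiased if all 10 have one. The number of procedures and the 80% are assumptions; only the 10 comes from the protocol.

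Because the protocol itself fixes the denominator, this is not merely a detail left to the SAP. It is nevertheless low priority. The endpoint is exploratory in a 10-patient pilot, carries no test or threshold, and leaves the primary conclusion unaffected.

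**What to change.** 1. In Sections 1.1, 3 and 9.1, make the main denominator the patients who were dosed, imaged under NIR and had SLN mapping or biopsy attempted.
2. Keep the all-enrolled rate as a secondary feasibility figure, and report both counts.
3. Reconcile Section 8.1.3 with the Schedule of Activities on whether SLN biopsy is discretionary.
4. Where the standard-of-care procedure identifies a sentinel node independently of CYTALUX, record that per node on the Appendix 1 form and report how often the same node fluoresced. The protocol names no such mapping method, so this item applies only where one is used.

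The cost is a smaller denominator, with the wider uncertainty that brings (perfect detection in 4 of 4 still has a lower limit of 40%), and one added data field. Items 1 to 3 are wording changes; item 4 also needs data capture in theatre.
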